11.4.1.1.2. Serious Adverse Events

A serious adverse event is an adverse event that falls into one or more of the following categories:

Tiziana Life Sciences, PLC - Confidential Page 65 of 101

- Results in death
- Is life-threatening, i.e., is an event which, in the view of the Investigator, places the subject at immediate risk of death from the event as it occurred (it does not include an event which hypothetically might have caused death if it was more severe)
- Requires inpatient hospitalization or prolongation of existing hospitalization
- Results in persistent or significant disability/incapacity, where disability is defined as a substantial disruption of a person's ability to conduct normal life functions, either reported or defined as per clinical judgment
- Is a congenital anomaly/birth defect (if exposure to product just before conception or during pregnancy resulted in an adverse outcome in the child)
- Is any other important medical event, i.e., may not result in death, be life-threatening, or require hospitalization, but based upon appropriate medical judgment, it may jeopardize the subject and may require medical or surgical intervention to prevent one of the outcomes listed in the points above. Examples of such events include allergic bronchospasm requiring intensive treatment in an emergency room or at home, and blood dyscrasias or convulsions that do not result in inpatient hospitalization.

A non-serious adverse event is any adverse event that does not meet the criteria listed above for a serious adverse event or the outcome (i.e., subject treatment, life-threatening condition, hospitalization, recovery) cannot be determined with the information provided.

Each adverse event has to be classified by the Investigator as serious or non-serious. This classification of seriousness of the event determines the reporting procedures to be followed.

In this trial the following do not have to be classified as Serious Adverse Events:

- Admission to hospital required by the protocol.
- Events definitely related to disease progression.

All deaths occurring during the reporting period have to be reported as SAEs, even if due to disease progression.

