After approval of Amendment 4 to the protocol, only SAEs should be reported to CLIOSS Pharmacovigilance for patients still receiving study treatment, up to 28 days after discontinuation of milciclib, according to Section 9.5.

Tiziana Life Sciences, PLC - Confidential Page 43 of 101

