11.4.1.3. Adverse Event Reporting Period

Adverse event reporting period:

The adverse event reporting period for this trial begins upon signing of informed consent form and ends 28 days after the last treatment administration.

.

However, if the patient begins a new anticancer therapy before 28 days after the last dose of study treatment administration, the adverse event reporting period will end at the time the new treatment is started.

All adverse events that occur in trial subjects during the adverse event reporting period must be reported to CLIOSS (delegated by the Sponsor), whether or not the event is considered related to the study treatment.

Adverse event follow up after the end of the reporting period:

The following events should be followed after the end of the reporting period (i.e., 28 days after the last treatment administration):

1. All serious adverse events with outcome "not recovered" or "unknown" at the end of the reporting period.

2. Those non-serious events whose relationship with investigational study treatment has been classified as "Unlikely", "Possible", "Probable" and "Definite" with outcome ' not recovered' at the end of the reporting period.

Such events should be followed until they resolve, the patient begins a new anticancer therapy or the Investigator determines, whenever possible, that they have become "chronic" or "stable". Resolution of such events is to be documented on the appropriate report form.

In addition, if, after the end of the reporting period, suspected serious adverse reactions or deaths are reported to the Investigator and he/she believes that they are related to the investigational product, it is the Investigator's responsibility to report this suspected serious adverse reactions to CLIOSS Pharmacovigilance. Such suspected serious adverse reactions will be reported using a Serious Adverse Event Report Form or any other way chosen by the Investigator.

After the cut-off date of 31 May 2017 and protocol Amendment 4 approval, SAEs will continue to be reported to CLIOSS Pharmacovigilance for patients continuing treatment, until 28 days after study treatment is discontinued, according to Section 9.5.

Tiziana Life Sciences, PLC - Confidential Page 67 of 101

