11.4.1.4. Reporting Requirements

Each adverse event has to be classified by the Investigator as SERIOUS or NON SERIOUS. The seriousness of the event determines the reporting procedures to be followed. If a serious adverse event occurs, the CLIOSS Pharmacovigilance (delegated by the Sponsor) has to be notified, by Fax ([name]) or by e-mail ([contact]) using the designated form, within 24 hours of awareness of the event by the Investigator. The initial report should be followed by submission of more detailed adverse event information within 5 calendar days after the Investigator first became aware of the serious adverse event. Reporting requirements for adverse events are summarized in the following table.

Table 8. Reporting requirements for adverse events			
Gravity	Reporting Time	Type of Report	
	Within 24 hours	Initial report on designated serious adverse event	
SEDIOUS		form (SAER-F)	
SERIOUS	Within 5 calendar days	Follow-up/Final report on designated serious	
		adverse event form (SAER-F)	
NONSERIOUS	Per case report form submission	Study case report forms	
	procedure		

Table 8. Reporting requirements for adverse events

Serious adverse events should also be recorded on appropriate section of the case report form.

In the rare event that the Investigator does not become aware of the occurrence of a serious adverse event immediately (for example, if an outpatient trial subject initially seeks treatment elsewhere), the Investigator should report the event within 24 hours after learning of it and document his/her first awareness of the adverse event.

Non serious adverse events have to be recorded on the study case report forms.

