11.4.1.5. Recording Adverse Events in the Case Report Forms

Information on adverse events must be evaluated by a physician and recorded in a source document such as the hospital file. Adverse events are to be recorded on the case report forms as above specified. The Investigator will also be asked to assess the relationship between the adverse event and the investigational medication.

• Preexisting Conditions

In this trial, a pre-existing condition (i.e., a disorder present before an adverse event occurs and recorded on the pretreatment medical history/physical examination form) should not be reported as an adverse event unless the condition worsens or episodes increase in frequency during the adverse event reporting period.

• Baseline Signs and Symptoms

Tiziana Life Sciences, PLC - Confidential Page 68 of 101

Milciclib maleate (PHA-848125AC)	CDKO-125a-006-P4
Protocol for Study CDKO-125a-006	09 March 2017

All Signs and Symptoms (either tumor-related or not tumor-related) collected at baseline should not be reported anymore during the study except in case they worsen in severity or in frequency.

• Procedures

Diagnostic and therapeutic non-invasive and invasive procedures, such as surgery, should not be reported as adverse events. However, the medical condition for which the procedure was performed should be reported if it meets the definition of adverse event. For example, an acute appendicitis that begins during the adverse event reporting period should be reported as the adverse event and the resulting appendectomy should be recorded in the source documents.

After cut-off date of 31 May 2017, AE/SAE data will be no longer collected into the CRF, but assessments information should continue to be collected into the patient's medical notes.

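### Section 11.4.1.1.2 makes an event non-serious when life threat or hospitalization cannot be determined, so some possible SAEs miss the 24-hour report and, after the cut-off, wait in site notes

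*Protocol*

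**What the plan says.** Section 11.4.1.1.2 lists the seriousness criteria, which include life threat, inpatient hospitalization and other important medical events. It then defines a non-serious event as one that meets none of them, "or the outcome (i.e., subject treatment, life-threatening condition, hospitalization, recovery) cannot be determined with the information provided". It adds: "This classification of seriousness of the event determines the reporting procedures to be followed".

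Section 11.4.1.4 and Table 8 set the two routes. A serious event is notified to pharmacovigilance "within 24 hours of awareness of the event by the Investigator", with a more detailed report within 5 calendar days. For the rest, "Non serious adverse events have to be recorded on the study case report forms", and Table 8 gives their timing only as the CRF submission procedure.

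Section 11.4.1.3 says which events are followed beyond the reporting period. One group begins: "All serious adverse events with outcome 'not recovered' or 'unknown". The other is non-serious events with any degree of relationship from unlikely to definite, but only if the outcome is 'not recovered'.

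For the period after the data cut-off, section 11.4.1.5 says: "After cut-off date of 31 May 2017, AE/SAE data will be no longer collected into the CRF". Information continues to be kept in the patient's medical notes. A footnote to the section 7 schedule says that, once Amendment 4 is approved, "only SAEs should be reported to CLIOSS Pharmacovigilance for patients still receiving study treatment".

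**The concern.** A seriousness rule has to say what happens when the first information is incomplete. This one resolves the doubt as non-serious, and it names two seriousness criteria among the things that may be undetermined. Lack of information therefore moves an event out of the expedited route at the point where the sponsor might still help to clarify it.

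The setting makes such reports plausible. Treatment is taken at home (section 9.1.2). Under section 5, patients beyond 6 cycles may attend once every 3 cycles, that is every 3 × 14 = 42 days, with a phone interview at the other two cycle ends. Section 11.4.1.4 itself foresees incomplete knowledge: "for example, if an outpatient trial subject initially seeks treatment elsewhere". At stake is how soon the sponsor hears of a possible SAE and, after the cut-off, whether it hears of it at all while the doubt lasts.

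**Working it through.** There is no figure to recompute. The check follows one event through the protocol's own rules.

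**Test event.** A patient is taken to another hospital with vomiting. The investigator hears of it but does not know whether the patient was admitted, and does not judge it life-threatening or an important medical event.

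1. **Classification (11.4.1.1.2).** No criterion is known to be met, and hospitalization cannot be determined. The second limb of the non-serious definition applies in terms, so the label is non-serious.
2. **Route before the cut-off (11.4.1.4, Table 8).** The event goes on the CRF at the pace of CRF submission, for which this section gives no number of days. Had the doubt been resolved the other way, it would have reached pharmacovigilance within 24 hours, with a follow-up report by day 5.
3. **Route after the cut-off (9.5, 11.4.1.3, 11.4.1.5, section 7 footnotes).** The CRF no longer takes AE data, and only SAEs go to pharmacovigilance for patients still on treatment. The event is neither, so it stays in the medical notes. (The trigger is worded variously as the cut-off date, Amendment 4 approval and, in footnote 14, Amendment 5 approval. The end state is the same.)
4. **Follow-up beyond the reporting period (11.4.1.3).** A serious event of unknown outcome is followed. A non-serious event is followed only if 'not recovered'. If recovery is also unknown, the test event falls outside both groups.
5. **Consistency of the definition.** The parenthesis also lists recovery. Read literally, an admitted patient whose recovery is unknown meets a seriousness criterion and the second limb of the non-serious definition at once. Section 11.4.1.3 treats such an event as serious. The two sections therefore collide, though only on outcome in the sense of recovery.
6. **When the gap closes.** Once the investigator learns that a criterion is met, the event is an SAE and the 24-hour duty in 11.4.1.4 runs from that moment. If that never becomes known, the event is never reported as serious.

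**The case against.** The case on the other side is that this is loose drafting with limited reach. Several parts of it stand.

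- **The important-medical-event criterion takes many events out of the clause.** It rests on medical judgment and does not need admission to be known. A reader might take convulsions with unknown admission as the obvious example of the gap. The text does not support that, because 11.4.1.1.2 names convulsions without inpatient hospitalization among its examples of important medical events. Deaths in the reporting period are always SAEs.
- **The 24-hour report is not the sponsor's only early signal.** With no data monitoring committee (12.5), a reader might infer that it is. But Table 4 asks the investigator to discuss grade 2 or higher tremors and other grade 2 or higher neurological toxicity with the sponsor. Table 4 and section 9.4.4 add failure to recover and delays beyond 2 weeks, and section 9.4.5 adds overdose. None depends on the seriousness label, and section 9.5 does not suspend them. They do not cover everything: the vomiting and diarrhea rows of Table 4 call for no sponsor discussion.
- **The conflict with 11.4.1.3 is narrow.** Its 'unknown' is the recovery status of an event already classed as serious, a different question from whether life threat or admission can be established. That section suggests the authors did not mean missing outcome data to cancel seriousness.
- **Section 11.4.1.3 also says that all adverse events in the reporting period go to CLIOSS.** Before the cut-off this does not set a 24-hour clock for a non-serious event. Afterwards the specific text limiting reports to SAEs takes over.
- **The investigator may call the patient in when in doubt (section 5).** This can shorten the uncertainty but does not change the label while it lasts. After Amendment 4, visits follow routine practice or investigator discretion, so the phone-interview setting and the post-cut-off gap should not simply be added together.

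These points narrow the set of affected events. None of them changes the default for an event that remains in it.

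**Conclusion.** The point holds. The protocol states a default that sends an event of undeterminable seriousness away from the 24-hour route. The size is a delay: from 24 hours to routine CRF timing before the cut-off, and until a criterion becomes known after it. It applies to events that no other criterion catches. The number of such events cannot be estimated from the document. The conclusion assumes that sites apply the definition as written.

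Two stronger readings should not be drawn. First, a reader might infer that after the cut-off these events are recorded nowhere. They remain in the site's medical notes and become reportable within 24 hours once a criterion is known; what is missing in the meantime is a route to the sponsor or pharmacovigilance. Second, a reader might infer that the SAE counts under section 12.3.6 are generally lowered. Before the cut-off the event is on the CRF and can be reclassified, so counts fall only for events never reclassified before the cut-off. Afterwards CRF collection stops for serious and non-serious events alike, so the clause changes no CRF-based count.

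This is a safety-reporting correction that should be made. It does not touch the primary analysis.

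**What to change.** In section 11.4.1.1.2, end the non-serious definition after the limb about failing the listed criteria, and delete everything from the 'or' that introduces the undetermined outcome. Add there, and in Table 8: 'An event whose seriousness cannot be determined from the available information is reported as serious within 24 hours and may be downgraded in the follow-up report.' Table 8 already provides for a follow-up report within 5 calendar days, so the means of downgrading exists. The change also removes the overlap with section 11.4.1.3, because unknown recovery would no longer be a ground for the non-serious label.

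The cost is one deleted clause, one added sentence in two places, and a few initial SAE reports later downgraded. Only reporting classification changes; treatment and clinical management do not.

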11.4.1.2. Eliciting Adverse Event Information

The Investigator has to report all directly observed adverse events and all adverse events spontaneously reported by the trial subject using concise medical terminology. In addition, each trial subject will be questioned about adverse events at each clinic visit following the signature of the informed consent. The question asked will be "Since your last clinical visit have you had any health problems?"

Tiziana Life Sciences, PLC - Confidential Page 66 of 101

11.4.1.3. Adverse Event Reporting Period

Adverse event reporting period:

The adverse event reporting period for this trial begins upon signing of informed consent form and ends 28 days after the last treatment administration.

.

However, if the patient begins a new anticancer therapy before 28 days after the last dose of study treatment administration, the adverse event reporting period will end at the time the new treatment is started.

All adverse events that occur in trial subjects during the adverse event reporting period must be reported to CLIOSS (delegated by the Sponsor), whether or not the event is considered related to the study treatment.

Adverse event follow up after the end of the reporting period:

The following events should be followed after the end of the reporting period (i.e., 28 days after the last treatment administration):

1. All serious adverse events with outcome "not recovered" or "unknown" at the end of the reporting period.

2. Those non-serious events whose relationship with investigational study treatment has been classified as "Unlikely", "Possible", "Probable" and "Definite" with outcome ' not recovered' at the end of the reporting period.

Such events should be followed until they resolve, the patient begins a new anticancer therapy or the Investigator determines, whenever possible, that they have become "chronic" or "stable". Resolution of such events is to be documented on the appropriate report form.

In addition, if, after the end of the reporting period, suspected serious adverse reactions or deaths are reported to the Investigator and he/she believes that they are related to the investigational product, it is the Investigator's responsibility to report this suspected serious adverse reactions to CLIOSS Pharmacovigilance. Such suspected serious adverse reactions will be reported using a Serious Adverse Event Report Form or any other way chosen by the Investigator.

After the cut-off date of 31 May 2017 and protocol Amendment 4 approval, SAEs will continue to be reported to CLIOSS Pharmacovigilance for patients continuing treatment, until 28 days after study treatment is discontinued, according to Section 9.5.

Tiziana Life Sciences, PLC - Confidential Page 67 of 101

11.4.1.4. Reporting Requirements

Each adverse event has to be classified by the Investigator as SERIOUS or NON SERIOUS. The seriousness of the event determines the reporting procedures to be followed. If a serious adverse event occurs, the CLIOSS Pharmacovigilance (delegated by the Sponsor) has to be notified, by Fax ([name]) or by e-mail ([contact]) using the designated form, within 24 hours of awareness of the event by the Investigator. The initial report should be followed by submission of more detailed adverse event information within 5 calendar days after the Investigator first became aware of the serious adverse event. Reporting requirements for adverse events are summarized in the following table.

Table 8. Reporting requirements for adverse events			
Gravity	Reporting Time	Type of Report	
	Within 24 hours	Initial report on designated serious adverse event	
SEDIOUS		form (SAER-F)	
SERIOUS	Within 5 calendar days	Follow-up/Final report on designated serious	
		adverse event form (SAER-F)	
NONSERIOUS	Per case report form submission	Study case report forms	
	procedure		

Table 8. Reporting requirements for adverse events

Serious adverse events should also be recorded on appropriate section of the case report form.

In the rare event that the Investigator does not become aware of the occurrence of a serious adverse event immediately (for example, if an outpatient trial subject initially seeks treatment elsewhere), the Investigator should report the event within 24 hours after learning of it and document his/her first awareness of the adverse event.

Non serious adverse events have to be recorded on the study case report forms.

11.4.1.5. Recording Adverse Events in the Case Report Forms

Information on adverse events must be evaluated by a physician and recorded in a source document such as the hospital file. Adverse events are to be recorded on the case report forms as above specified. The Investigator will also be asked to assess the relationship between the adverse event and the investigational medication.

• Preexisting Conditions

In this trial, a pre-existing condition (i.e., a disorder present before an adverse event occurs and recorded on the pretreatment medical history/physical examination form) should not be reported as an adverse event unless the condition worsens or episodes increase in frequency during the adverse event reporting period.

• Baseline Signs and Symptoms

Tiziana Life Sciences, PLC - Confidential Page 68 of 101

Milciclib maleate (PHA-848125AC)	CDKO-125a-006-P4
Protocol for Study CDKO-125a-006	09 March 2017

All Signs and Symptoms (either tumor-related or not tumor-related) collected at baseline should not be reported anymore during the study except in case they worsen in severity or in frequency.

• Procedures

Diagnostic and therapeutic non-invasive and invasive procedures, such as surgery, should not be reported as adverse events. However, the medical condition for which the procedure was performed should be reported if it meets the definition of adverse event. For example, an acute appendicitis that begins during the adverse event reporting period should be reported as the adverse event and the resulting appendectomy should be recorded in the source documents.

After cut-off date of 31 May 2017, AE/SAE data will be no longer collected into the CRF, but assessments information should continue to be collected into the patient's medical notes.

11.4.1.6. Grading of Adverse Event Severity

The severity of adverse events will be graded using the Common Terminology Criteria for Adverse Events (CTCAE, Version 3.0) of the US National Cancer Institute. See the website: http://ctep.info.nih.gov/reporting/ctc.html. For each event, the highest severity grade attained should be reported.

Schedule of adverse events safety assessment is reported in Section 7, Schedule of Events.

For events not reported in the CTCAE Version 3.0, the Investigator will use the grade or adjectives reported in Table 9:

Grade	Adjective	Description
Grade 1	Mild	Does not interfere with patient's usual function
Grade 2	Moderate	Interferes to some extent with patient's usual function
Grade 3	Severe	Interferes significantly with patient's usual function
Grade 4	Life-threatening	Results in threatening to life or in an incapacitating disability
Grade 5	Death	Results in death

Table 9. Grading of Adverse Event Severity for Events not reported in the CTC	AE
Version 3.0	

Note the distinction between the seriousness and the intensity of an adverse event. Severe is a measure of intensity; thus, a severe reaction is not necessarily a serious reaction. For example, a headache may be severe in intensity but would not be classified as serious unless it met one of the criteria for serious events listed in paragraph (see Section 11.4.1.1.2).

